While almost nothing is known about urinary/vaginal microbiome interplay, even less is known about immune response modulation in the bladder and vagina. However, estrogen reduces the subsequent UTI rate in hypoestrogenic women affected by recurrent UTI [9, 10], and estrogen induces urothelial antimicrobial peptide (AMP) expression [15]. Since AMPs exhibit microbicidal activity, stimulate inflammation, and facilitate epithelial barrier homeostasis [11], estrogen may work through AMPs as mediators to optimize microbial equilibrium.

**We hypothesize that, following estrogen treatment of hypoestrogenic women with OAB, symptom improvement will be associated with 1) reduced FUM diversity, 2) alteration of other FUM characteristics and 3) increased AMP levels.** We propose two specific aims:

**Aim 1: To compare pelvic floor microbiome (PFM) diversity and AMP levels before and after estrogen treatment in hypoestrogenic women with OAB symptoms.**

We will enroll 20 hypoestrogenic patients with bothersome OAB prior to clinically indicated vaginal estrogen treatment as part of a pilot study. We will collect catheterized urine, voided urine, perineal swabs, vaginal swabs and vaginal lavage at baseline and 12 weeks post treatment. We will assess the associated PFMs (i.e. urinary and vaginal microbiomes) using two complementary approaches: (i) Expanded Quantitative Urine Culturing (EQUC) and/or (ii) 16S rRNA amplicon sequencing. We will quantify candidate AMPs by quantitative PCR and protein analysis [12, 13]. We will compare and contrast each PFM and its associated AMP profiles. Relevant questions include: Do associations exist amongst adjacent PFMs and between PFMs and AMPs? Do PFMs and AMPs change in response to estrogen? Does an improved (less diverse) PFM correlate with an optimized AMP profile?

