**Aim 2: Determine if FUM characteristics correlate with OAB symptoms.**

At baseline and 12 weeks, we will use the overactive bladder questionnaire (OAB-q) [14] to evaluate symptoms and determine if PFM characteristics (e.g., composition, diversity, abundance, specific organisms) and AMP levels (gene expression and protein levels) correlate with patient symptoms. Relevant questions include: Does response to estrogen associate with pre-treatment PFM and/or AMP characteristics? Do PFM and/or AMP changes correlate with treatment response?

**Significance:** The medical field is beginning to adopt treatments that alter an individual's microbiome and AMP profile to improve patient health; however, this approach has not been adopted for LUTS treatment. Here, we propose the first step in development of such a therapy. If our hypothesis is correct, we could validate estrogens a first line of treatment in hypoestrogenic women. It could also propel the use of an individual's PFM and/or AMP characteristics to develop future personalized therapies to improve treatment response and/or prevent LUTS.

[figure not shown]
**Estrogen improves OAB symptoms:** There is compelling evidence to suggest that vaginal estrogen therapy relieves symptoms of OAB including frequency, urgency and UUI in postmenopausal women [7, 8, 11, 12]. The evidence is sufficient to list the application of vaginal estrogen alone as a treatment option for OAB in the clinical practice guidelines for postmenopausal women with urogynecological complaints [18]. The mechanism of vaginal estrogen's effect on OAB symptoms is poorly understood. Vaginal estrogen has the ability to modify the vaginal microbiome and reduce recurrent urinary tract infections in postmenopausal women [16]. We reason that vaginally applied estrogen would also modify the FUM, which appears to play a role in OAB [1].

**The Bladder is Not Sterile.** Current treatments and preventive strategies are based upon the dogma that the bladder is a sterile environment. Compelling new evidence challenges this long-held belief. Detection of bacterial DNA and isolation of live bacteria from urine taken directly from the bladders of women with and without urinary symptoms has been reported by us [1-3], and by others [4, 5]. However, the role of the female urinary microbiome (FUM) in urinary health and disease is incompletely understood.

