**FUM diversity correlates with symptoms.** Recently, we sequenced and cultured urines from individuals with urgency urinary incontinence (UUI) and continent controls using two complementary methods, 16S rRNA sequencing and expanded quantitative urine culturing (EQUC) [1]. We observed a striking difference in the diversity between the two cohorts (**Figure 1**). Continent controls had a markedly less diverse FUM than did the UUI cohort (1 [interquartile range (IQR) = 1 to 2] versus 3 [IQR = 1-7],  $p=0.0001$ ). This suggests that a healthy FUM is a less diverse FUM. By decreasing FUM diversity, we might be able to improve patient symptoms.

**Vaginal and bladder microbiomes are similar.** The vaginal microbiome is characterized by five dominant genera or species; these groups are called community state types (CSTs). Four of the five CSTs are low diversity microbiomes dominated by different *Lactobacillus* species, making *Lactobacillus* the most commonly found organism in the vagina. The final CST (CST IV) is a diverse mixed community dominated by anaerobes such as *Gardnerella*, *Prevotella*, and *Aerococcus* [19]. The organisms found in the bladder tell a very similar story. The FUM of the majority of individuals is dominated by *Lactobacillus*, with another group dominated by one or more anaerobes, such as *Gardnerella*, *Prevotella*, and *Aerococcus* [1]. This similarity in bacterial composition and the anatomical proximity of these two biological niches, lead us to reason that bacteria of bladder and vagina might behave similarly. A major factor in determining the health of the vaginal microbiota is estrogen.

**Fig 1: UUI communities are more diverse than non-UUI controls.** A rarefaction analysis showing the number of unique species of bacteria isolated (using EQUC) with each new patient sampled. More unique species of bacteria are seen in the UUI population than the non-UUI controls.

**Diversity of the vaginal microbiome changes in response to estrogen.** The majority of healthy premenopausal women have low diversity vaginal microbiomes dominated by *Lactobacillus* [19]. A small percentage of women have a higher diversity microbiome dominated by anaerobes [19]. Following menopause, many women lose *Lactobacillus* and their vaginal microbiomes become more diverse and anaerobic. However, this change can be reversed with estrogen treatment. Since the vagina and bladder have

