## Methodology

**Power Calculation/Sample Size:** Based on the difference in diversity between UUI and non-UI controls (Fig 1), we were able to do a power analysis and determine that a sample size of 60 will give us sufficient power (0.816), using the Wilcoxon-Mann-Whitney test, to detect the difference between patients whose urinary microbiomes retain high diversity compared to those that change to a low diversity state. Initially, we plan to conduct a pilot study of 20 patients to inform a future, larger funded study.

**Recruitment:** Women will be recruited from the ambulatory urogynecology clinic at Loyola University Medical Center. A total of 60 hypoestrogenic, post-menopausal women will be enrolled as part of a pilot study. The PFM and AMPs will be measured prior to, and following 12 weeks of, vaginal estrogen treatment. Each patient will act as her own control, with her own baseline prior to estrogen treatment. Subjects who meet eligibility criteria and agree to research participation will indicate their consent by signing the research consent form. Subjects will indicate their consent for biorepository storage of leftover urine for potential future IRB-approved studies by signing the biorepository consent form. Consistent with prevalent research regulations and policies, a signed copy of the research and biorepository consent documents will be given to the subject and the investigator will keep the original research consent documents. Participation in the research will not depend upon participation in the biorepository (**Appendix 1**). Please see the ethics and patient consent section for details of the consent process.

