### ***Patient Data Collection:***

**Visit 1 (baseline):** After enrollment and informed consent is obtained, patients will be asked to complete the OAB-q, a validated questionnaire, (**Appendix 3**) to measure OAB-related symptoms and quality of life [17]. Voided urines will be collected in a hat for 16SrRNA, PCR and protein analysis. A perineal swab will then be collected and assessed by 16S rRNA sequencing. Then a 30 mL vaginal lavage will be collected from the anterior wall of the vagina using sterile water for PCR and protein analysis. A vaginal swab will also be collected from the posterior fornix prior to the catheterized urine collection and assessed by 16S rRNA sequencing. Following the collection of the vaginal swab, a post void residual specimen will be collected by transurethral catheter, which is part of our standard practice for new patients. This specimen will be sent for standard clinical microbiology culture, EQUC and 16S rRNA gene evaluation. The specimens destined for the [name] lab will be stored on ice until pick up and transport. The swabs and urine for culture will be stored at room temperature until processed. The urine for sequencing will be refrigerated.

Demographic information and clinical characteristics will be collected, including age, parity, medical illness, previous hysterectomy, previous incontinence surgery, post void residual volume and body mass index (**Appendix 4**).

Physical examination will be completed, including evaluation for pelvic organ prolapse with the POP-q examination, which is part of a standard initial clinical evaluation.

Patients will be counseled on the evidence-based, first-line options for the treatment of OAB, including behavioral modifications, physical therapy, and vaginal estrogen per standard practice in our clinic. All study participants will be provided vaginal estrogen Premarin Cream® 0.625 mg conjugated estrogen/gram and instructed to use 0.5 grams twice weekly with the applicator. This is based on the clinical practice guidelines for vaginal estrogen use in postmenopausal women with urogynecological complaints developed by the Society of Gynecological Surgeons Systematic Review Group [18]. Patients will receive compensation at visit one with a parking voucher.

Patients will be given a medication diary for the use of vaginal estrogen to assess compliance (**Appendix 5**).

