Statistical analyses of the microbiome data (EQUC and 16S rRNA) will be performed using SAS software version 9.4. Descriptive statistics for demographics, clinical characteristics, and microbiome data will be calculated including means with standard deviations, medians with interquartile ranges, or counts and percentages. Medians and interquartile ranges will be presented for OAB-q subscales at each time point as well as a change score, and Wilcoxon signed-rank tests assessed statistical significance of change in OAB-q. Each diversity measure will be modeled as a separate dependent variable in a linear mixed-effects regression, with independent variables including time, OAB-q symptom severity, physical therapy completed, weeks of estrogen compliance, and body mass index, and random intercepts for subjects. Spearman's rho will be calculated for change in Lactobacillus levels associated with change in the OAB-q symptom severity (12-week minus baseline values). For AMP data analyses, Spearman's rho will be used to test associations between change in relative abundance and change in area of bacterial growth inhibition.

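### Aim 1 asks for the before-after change in diversity, but the only planned test of diversity adjusts its time effect for OAB-q symptom severity

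*Combined protocol and SAP*

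**What the plan says.** Specific Aims gives Aim 1 as: "To compare pelvic floor microbiome (PFM) diversity and AMP levels before and after estrogen treatment in hypoestrogenic women with OAB symptoms". Recruitment (Methodology) describes a paired design: "Each patient will act as her own control, with her own baseline prior to estrogen treatment". The hypothesis is that "symptom improvement will be associated with 1) reduced FUM diversity", and Expectations predicts outright that estrogen will lower bladder diversity and improve symptoms.

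Under Statistical Analysis Plan, each diversity measure is the outcome of a linear mixed model with random subject intercepts, "with independent variables including time, OAB-q symptom severity, physical therapy completed, weeks of estrogen compliance, and body mass index". The text does not say which visit's OAB-q score is used. The same paragraph plans a signed-rank test of change for OAB-q only. It plans Spearman correlations for Lactobacillus change and for the AMP data, and descriptive statistics for the rest of the microbiome data.

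Aim 2 is the association question: to "determine if PFM characteristics (e.g., composition, diversity, abundance, specific organisms") and AMP levels correlate with symptoms.

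**The concern.** Aim 1 needs the within-woman change in diversity without conditioning on symptoms. The planned model holds symptom severity fixed, and severity is itself expected to change after treatment and to move with diversity. If the sponsor's hypothesis is right, the model subtracts part of the effect that Aim 1 looks for.

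If the time coefficient is then reported as the before-after result, a partial fall in diversity can be missed or given the wrong sign. A rise can also be declared when diversity has not changed. The pilot is meant to inform a larger study, so such an estimate would be carried forward.

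**Working it through.** **1. The plan's own figure.** The one stated power is 0.816 at N = 60 (Power Calculation/Sample Size), "using the Wilcoxon-Mann-Whitney test, to detect the difference between patients whose urinary microbiomes retain high diversity compared to those" that change to low diversity. This is an unpaired contrast, and the analysis plan does not take it up. With SD = IQR/1.349 and 30 per group, a two-sided normal approximation gives 0.62 to 0.68. A simulated Mann-Whitney test on counts with the quoted quartiles gives 0.79 to 0.89, depending on the tails. The split and sidedness are not stated, so 0.816 can be neither confirmed nor refuted. Nothing below depends on it.

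**2. What the time coefficient estimates.** Take two visits, complete pairs, same-visit OAB-q, and the other covariates constant per woman. The estimating equation for time sets the sum of within-woman residual differences to zero:

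mean(ΔD) − τ − β × mean(ΔOAB-q) = 0, so **τ = mean(ΔD) − β × mean(ΔOAB-q)**.

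Here ΔD is diversity change, τ the time coefficient and β the OAB-q slope. The identity held to below 1e-14 in every simulated dataset. If lower severity goes with lower diversity (β > 0) and severity falls, τ lies above the true change. Hand check in SD units, with severity falling by 1 and equal within- and between-woman correlations r, so that β = r:
- True change −0.50: τ = −0.50 + r, giving −0.50, −0.30 and −0.10 at r = 0, 0.2 and 0.4.
- True change −0.25: τ = −0.25, −0.05 and +0.15.
- No change: τ = 0, +0.20 and +0.40, an apparent rise.

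**3. Scale.** The background section gives EQUC species of 3 (IQR 1 to 7) in UUI and 1 (IQR 1 to 2) in controls.
- SDs: 6/1.349 = 4.4 and 1/1.349 = 0.74; pooled √((4.4² + 0.74²)/2) ≈ 3.2.
- The full gap of 2 species is 2/4.4 = 0.45 SD to 2/3.2 = 0.63 SD. Half the gap is 0.22 to 0.31 SD.
- Expectations foresees a smaller difference than in that earlier study.
- Completers at 7% loss: 60 × 0.93 = 55.8, about 56; 20 × 0.93 = 18.6, about 19.

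Not in the documents, so assumed: ICC 0.3 to 0.7, OAB-q improvement 0.5 or 1 SD, within-woman correlation r 0 to 0.4, and between-woman correlation either 0 or equal to r.

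**4. Simulation.** REML random-intercept model, 1000 replicates per cell, two-sided 5% tests; Monte Carlo error is about ±0.03 at power 0.5. Ranges run over ICC and between-woman correlation. Entries are the adjusted time coefficient with power in brackets, n = 56. Normal outcomes are in SD units and counts in species.

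| Scenario | Time-only power | r = 0 | r = 0.2 | r = 0.4 |
|---|---|---|---|---|
| Normal, fall 0.5, OAB-q 1 SD | 0.85–1.00 | −0.50 (0.76–0.95) | −0.37 to −0.29 (0.34–0.74) | −0.25 to −0.09 (0.08–0.44) |
| Normal, fall 0.25, OAB-q 1 SD | 0.33–0.68 | −0.25 (0.25–0.39) | −0.13 to −0.05 (0.06–0.15) | +0.01 to +0.15 |
| Counts, median 3 to 2, OAB-q 1 SD | 0.42–0.75 | −1.5 (0.34–0.46) | −1.0 to −0.6 (0.07–0.25) | −0.5 to +0.3 (0.04–0.09) |
| Counts, median 3 to 2, OAB-q 0.5 SD | as above | −1.5 (0.39–0.68) | −1.2 to −1.0 (0.22–0.47) | −1.0 to −0.6 (0.10–0.37) |

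Baseline counts are geometric with ratio 0.84 (quartiles 1, 3, 7; mean 0.84/0.16 = 5.25). The median-2 case has ratio 0.79 (mean 0.79/0.21 = 3.76), a mean change of −1.5.

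- Full fall to the control distribution (mean change −3.8): adjusted −3.5 to −2.5 at r = 0.2 to 0.4, power 0.92 to 1.00.
- No change in counts, 1 SD improvement: the adjusted test rejects in 10–25% (r = 0.2) and 31–71% (r = 0.4) of runs, nearly all as a rise. Time-only rejects in 4–6%.
- Baseline OAB-q score, normal, fall 0.5: −0.51 to −0.49, power 0.85 to 1.00.
- n = 19, normal, fall 0.5, 1 SD improvement: time-only 0.40 to 0.77; adjusted 0.31–0.48, 0.14–0.29 and 0.06–0.16 at r = 0, 0.2 and 0.4.

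**5. A second model.** Here severity depends on diversity with coefficient b (n = 55, ICC 0.5, OAB-q fall 0.8, true change −0.5). At b = 0, 0.2, 0.4 and 0.6 the adjusted estimates are −0.51, −0.34, −0.22 and −0.14, with power 0.90, 0.59, 0.33 and 0.18. Time-only power is 0.95 to 0.97. With no true change, the adjusted test rejects in 16% to 74% of runs for b = 0.2 to 0.6.

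**The case against.** - **OAB-q might be a baseline score.** With complete pairs the time term would then be unbiased. This stands as a condition. But the OAB-q is repeated at Visit 2, and the next sentence of the analysis plan uses the same variable as a 12-week minus baseline difference. A model with one row per visit most naturally takes that visit's value.
- **The hypothesis is an association, which the OAB-q coefficient addresses.** True, and that is why the model suits Aim 2. Aim 1 is still a before-after comparison, and Expectations predicts a fall in diversity.
- **Expectations sets p < 0.05 for a difference in species number, and descriptive statistics are planned.** No test is attached to that threshold. By-visit and change-score reporting is stated only for OAB-q.
- **The large effects rest on assumed inputs.** This stands. At r = 0 there is lost power but no bias. The sign reversals need r = 0.4 with a 1 SD improvement and only a partial fall.
- **Weeks of compliance may be the larger problem.** If coded 0 at baseline and about 11 at 12 weeks (assumed SD 1.5), it correlates 0.98 with time. The time-term SE is then about 0.88 against 0.16, and power 0.09 against 0.84, even at r = 0. The coding is unstated, so this strengthens the case for a time-only analysis.
- **Aim 1 also covers AMP levels, for which only correlations are planned.** This is a separate gap and stands.

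**Conclusion.** The concern holds and should be fixed before analysis. No planned inferential analysis estimates the Aim 1 diversity change free of symptom adjustment. On the same-visit reading of OAB-q, the direction of the bias follows from algebra together with the sponsor's own predictions.

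Its size depends on correlations that the documents do not give. A partial fall could be largely hidden or, at the upper end of the assumed range, reversed. A full fall to control values would be understated but still detected with 56 completers. Confidence is medium, because OAB-q timing and the coding of the other covariates are not stated.

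**What to change.** In the Statistical Analysis Plan:

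1. **Name one Aim 1 analysis per measure.** For the inverse Simpson and Shannon indices, use a random-intercept model with time as the only fixed effect, and report the time coefficient with its 95% CI. For the skewed EQUC species count, use a signed-rank test on the 12-week minus baseline count, with median change and IQR.
2. **Keep the existing model as the secondary, Aim 2 analysis.** State that OAB-q is the same-visit score and that its coefficient is the diversity-symptom association. State how weeks of use and physical therapy are coded.
3. **Examine physical therapy separately**, in a secondary regression of diversity change on therapy completed (0/1) and centred weeks of use.

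This needs no new data. The costs are:
- **Concurrent therapy.** Women are counseled on options "including behavioral modifications, physical therapy, and vaginal estrogen per standard practice in our clinic", so the Aim 1 estimate includes any therapy effect, equal to uptake × effect. Assuming 10–50% uptake and 0.1–0.3 SD, that is 0.1 × 0.1 = 0.01 to 0.5 × 0.3 = 0.15 SD. The secondary regression separates it with SE 0.14, 0.16 and 0.19 SD at 10%, 30% and 50% uptake, against 1/√56 = 0.13 for the paired change (n = 56, ICC 0.5).
- **Signed-rank test.** Power is 0.49–0.53 against 0.52–0.57 for the time-only model (n = 56, median 3 to 2, ICC 0.5), and it uses completers only.
- **Pilot size.** Low power at 20 patients remains.

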**Expectations:** Since the FUM is more diverse in women with UII than in women without UII, since the bacteria of the FUM are similar to those of the vagina, and since estrogen treatment can reverse the increased diversity of the vaginal microbiome associated with menopause, we predict that estrogen treatment will make the FUM less diverse and improve LUTS. On the basis of our recently published study [1], we expect that hypoestrogenic women with UII, on average, will have 3 different bacterial species as detected by EQUC. We predict that estrogen treatment will reduce this average number towards the average of 1 bacterial species as detected by EQUC in the continent controls from our previous study [1]. In that study, the difference between women with UII and women without UII was highly significant ( $p=0.0001$ ). In the proposed study, we anticipate a smaller difference (since all women will have UII) and will consider significance at  $p<0.05$ . Since 16S sequencing and EQUC provide complementary views of the FUM [1], we anticipate that sequencing will provide similar results; however, sequencing can identify bacteria that are not cultured, even by EQUC, and thus will provide us with a broader view of FUM composition. We predict that AMP levels will correlate with certain microbiota profiles, and anticipate that increased AMPs *via* estrogen supplementation will correlate with improved frequency and severity of OAB symptoms.

**Possible Limitations to the study:** We do not anticipate any problems recruiting and retaining patients, as we have a long track record of similar studies. We anticipate some loss to follow-up (~7%). The timing of the first sample, taken at the first visit, will be necessarily variable but will be about 12 weeks from the commencement of estrogen treatment.

We do not anticipate any problems in the transfer of samples from the Ambulatory Clinic to the Clinical Microbiology Lab or the Genomics Facility, respectively, for culture and sequencing, as we have an established

and successful protocol for such transfer. For similar reasons, we also do not anticipate problems with the culture or sequence analyses.

We know that some urinary bacteria do not grow, even under EQUIC conditions. We also know that some bacteria are not readily sequenced. However, the strengths and weaknesses of EQUIC and sequencing are complementary and thus permit a broad and relatively unbiased view of the bacterial composition of the FUM.

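### The plan hypothesises that symptom improvement goes with a fall in urinary microbiome diversity, but its only diversity–symptom analysis does not isolate that within-woman link

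*Combined protocol and SAP*

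**What the plan says.** - **Hypothesis (Specific Aims).** After estrogen treatment, "symptom improvement will be associated with 1) reduced FUM diversity". Both sides of this statement are changes in the same woman.
- **Aim 2.** The plan will "determine if PFM characteristics (e.g., composition, diversity, abundance, specific organisms" and AMP levels correlate with symptoms. One of its listed questions is "Do PFM and/or AMP changes correlate with treatment response".
- **Statistical Analysis Plan, diversity.** "Each diversity measure will be modeled as a separate dependent variable in a linear mixed-effects regression". The covariates named are visit time, one OAB-q severity score, physical therapy, estrogen compliance and BMI, and each woman has a random intercept. No change score, no split of OAB-q into within- and between-woman parts, and no time-by-OAB-q term is listed.
- **Statistical Analysis Plan, changes.** "Spearman's rho will be calculated for change in Lactobacillus levels associated with change in the OAB-q symptom severity", taken as 12-week minus baseline. OAB-q change is otherwise tested alone by signed-rank test. The AMP correlation does not involve OAB-q.
- **OAB-q reporting.** "Medians and interquartile ranges will be presented for OAB-q subscales at each time point as well as a change score". This makes a visit-specific OAB-q covariate the natural reading of the model, although the plan does not say so.
- **Expectations.** "We predict that estrogen treatment will reduce this average number towards the average of 1 bacterial species as detected by EQUC". The expected fall in diversity is stated on this measure.

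**The concern.** The plan applies a change-on-change correlation to Lactobacillus. That answers part of Aim 2, because specific organisms are among the listed microbiome characteristics. Diversity, the first element of the hypothesis, gets no such analysis.

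The OAB-q coefficient in the diversity model draws on two sources: whether a woman's diversity moves with her own symptoms, and whether more symptomatic women have more diverse microbiomes. Only the first bears on the hypothesis. If only the second were present, the coefficient could still be significant and be read as support. A between-woman link is plausible, since the background section reports higher diversity in women with UUI than in continent controls. The pilot is also meant to inform a larger study, which would need a clean estimate of the within-woman association.

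**Working it through.** **Inputs from the documents.** There are two visits per woman. The sample is 20 (Aim 1; Power Calculation/Sample Size) or 60 (Recruitment). Loss to follow-up is about 7% (Possible Limitations), and the significance level is 0.05 (Expectations). Complete pairs: 20 × 0.93 = 18.6, about 19; 60 × 0.93 = 55.8, about 56.

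**The plan's own figure.** The stated power of 0.816 with 60 women is for a Wilcoxon-Mann-Whitney contrast, not for this association. It can be neither confirmed nor refuted, because the group split, sidedness and full distribution are not given. Simulation matched to the quoted quartiles, with assumed tails, gives 0.53 to 0.90 for 60 in total. Nothing below depends on it.

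**What the single OAB-q term estimates.** Let r be the correlation of OAB-q between a woman's two visits and ρ that of the diversity residual. With a time term, the information on the within-woman slope is proportional to (1−r)/(1−ρ), and on the between-woman slope to (1+r)/(1+ρ). The fitted coefficient is therefore about w × between slope + (1−w) × within slope, with

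w = (1+r)(1−ρ) / [(1+r)(1−ρ) + (1−r)(1+ρ)].

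- r = ρ: w = 0.50.
- r = 0.2, ρ = 0.8: w = (1.2 × 0.2)/(1.2 × 0.2 + 0.8 × 1.8) = 0.24/1.68 = 0.14.
- r = 0.8, ρ = 0.2: w = 1.44/1.68 = 0.86.

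The between-woman share is not zero at any of these settings. The two slopes can stand in for each other only if they are equal.

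**False-positive rate with no within-woman link.** This was simulated with 4,000 replicates per cell (Monte Carlo SE at most 0.8 points). The model is random-intercept REML with time, visit-specific OAB-q, and woman-level physical therapy, compliance and BMI. The intraclass correlation (ICC) is the same for both variables. Between-woman correlations and ICCs are assumptions. Percent rejecting at 0.05, for ICC 0.3 / 0.5 / 0.7:

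| Between-woman correlation | 19 pairs | 56 pairs |
|---|---|---|
| 0 | 5.3 / 5.8 / 6.5 | 5.1 / 4.9 / 4.9 |
| 0.1 | 5.9 / 5.6 / 6.9 | 6.8 / 7.2 / 6.9 |
| 0.2 | 6.5 / 7.0 / 7.6 | 7.4 / 10.6 / 13.4 |
| 0.3 | 6.9 / 9.0 / 12.3 | 10.6 / 19.1 / 26.9 |

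In the same cells, Spearman on changes rejects in 4.5%–5.9% and the coefficient of OAB-q deviation from the woman's mean in 4.5%–5.7%. At correlation 0.3, 83%–94% (19 pairs) and 96%–100% (56 pairs) of the planned term's rejections point in the hypothesised direction.

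**Sensitivity.** With integer species counts (ICC 0.5), the planned term rejects in 7% and 9% (19 pairs) and 9% and 14% (56 pairs) at correlations 0.2 and 0.3. With unequal ICCs at correlation 0.3, OAB-q 0.3 and diversity 0.8 give 6% and 10%; the reverse pattern (0.8 and 0.3) gives 11% and 23%.

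**Power, within-woman correlation 0.3.**
- Between-woman correlation also 0.3: planned term 0.41–0.42 against Spearman on changes 0.21–0.22 (19 pairs); 0.88–0.89 against 0.57–0.58 (56 pairs).
- Between-woman correlation 0: 0.21–0.28 against 0.21–0.22 (19 pairs); 0.49–0.69 against 0.57 (56 pairs).

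**Precision.** The approximate 95% CI around rho = 0 is ± tanh(1.96 × √(1.06/(n−3))): ±0.47 for n = 19 and ±0.27 for n = 56.

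**The case against.** **A reader might infer that the plan has no analysis linking diversity to symptoms.** The documents do not support that. With two visits and a time term, the within-woman part of the OAB-q coefficient is the change-on-change regression. The list of covariates is also introduced as non-exhaustive. The accurate statement is that this part is not isolated.

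**A reader might infer that the planned test is badly inflated.** That does not hold at pilot size, and the larger figures need 56 pairs and a correlation of 0.3 that no document supplies. A between-woman slope of 0.5 (both variables with SD 1 and ICC 0.5) would give 30% and 68% rejections, but it is an arbitrary value. The only documented link is UUI against continent controls, and Expectations itself anticipates a smaller difference. How far the symptom range is narrowed is unclear. Expectations says all women will have UUI, while the Inclusion Criteria admit women without it. Possible Limitations cites an exclusion of severe UUI that the Exclusion Criteria do not list.

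**The planned model is legitimate.** It suits Aim 2's broader question of whether microbiome characteristics and symptoms correlate, and it is more powerful when both associations agree. This stands, and is why the model should stay.

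**Covariate coding is unstated.** Physical therapy and compliance could be entered as zero at baseline, and would then adjust the within-woman contrast. The blending remains: with that coding the term rejects in 11% (19 pairs) and 18% (56 pairs) at correlation 0.3.

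**Conclusion.** The point holds as a minor one. The hypothesis concerns change within women, and the plan's only diversity–symptom term blends that with differences between women.

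With no within-woman link, and allowing for repeat simulation runs, the term rejects in about 6%–9% (19 pairs) or 7%–14% (56 pairs) at a between-woman correlation of 0.2. At 0.3 it rejects in about 7%–13% or 10%–27%, mostly in the hypothesised direction. These figures assume equal ICCs of 0.3–0.7 and a visit-specific OAB-q covariate. The documents give no correlation or ICC. For 20 women the excess is a few points.

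The firmer argument is independent of those assumptions: at either sample size, the first element of the hypothesis has no estimate of its own.

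**What to change.** Keep the mixed model, describe it as an association of levels, and state that its OAB-q term is visit-specific. Add to the Statistical Analysis Plan:

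> To address the hypothesis that symptom improvement accompanies reduced urinary diversity, Spearman's rho with a 95% CI will be estimated between change in catheterized-urine diversity and change in OAB-q symptom severity (both 12-week minus baseline). EQUC species number is the lead measure; inverse Simpson and Shannon indices from catheterized-urine sequencing are supportive. Results are exploratory.

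EQUC species number leads because Expectations states the predicted fall on it. Naming one lead matters: with three measures and no link, the chance of at least one p<0.05 is 10%–15%.

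An alternative for the same target is to enter OAB-q as each woman's mean plus her visit deviation, and read the deviation coefficient for this hypothesis.

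**Cost.** A few sentences and no new data. Power is lower than for the blended term when both associations agree (both correlations 0.3): about 0.21 against 0.41 with 19 pairs, and 0.58 against 0.89 with 56. The interval is wide (about ±0.47 or ±0.27), so the pilot result is an estimate rather than a test. The simple correlation also leaves shared causes in place. If physical therapy shifted both changes by 0.8 SD (an assumption), it would reject in 8.5% (19 pairs) or 15.8% (56 pairs) with no other link. With no control arm either, no causal claim should be made.
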